- me (including, if applicable, my spouse [or legal partner] and dependent children)
- my subinvestigators (including, if applicable, their spouses [or legal partners] and dependent children)

at the start of the study and for up to one year after the study is completed, if there are changes that affect my financial disclosure status.

I agree to ensure that the confidential information contained in this document will not be used for any purpose other than the evaluation or conduct of the clinical investigation without the prior written consent of Amgen Inc.

Signature

Name of Investigator

Date (DD Month YYYY)

Approved

Protocol Synopsis

Title: Open-label, Single-Arm, Multicenter Study to Evaluate the Safety, Tolerability and Efficacy of Evolocumab for LDL-C Reduction, as Add-On to Diet and Lipid Lowering Therapy, in Pediatric Subjects From 10 to 17 Years of Age With Heterozygous Familial Hypercholesterolemia (HeFH) or Homozygous Familial Hypercholesterolemia (HoFH) HAUSER-OLE

Study Phase: 3b

Indication: Heterozygous familial hypercholesterolemia or homozygous familial hypercholesterolemia in pediatric subjects 10 to 17 years of age

Primary Objective: To describe the safety and tolerability of 80 weeks of SC evolocumab when added to standard of care in pediatric subjects 10 to 17 years of age with HeFH or HoFH

Secondary Efficacy Objectives:

- To describe percent change and change from baseline in LDL-C, and on percent change from baseline in non-high-density lipoprotein cholesterol (non-HDL-C), apolipoprotein B (ApoB), total cholesterol/HDL-C ratio, and ApoB/Apolipoprotein A-1 (ApoA1) ratio, in pediatric subjects 10 to 17 years of age with HeFH or HoFH after 80 weeks of SC evolocumab, added to standard of care in pediatric subjects 10 to 17 years of age with HeFH or HoFH

Secondary Safety Objectives:

- To describe change from baseline in steroid hormones and the subject incidence of abnormal muscle and liver enzyme levels after 80 weeks of SC evolocumab, added to standard of care in pediatric subjects 10 to 17 years of age with HeFH or HoFH
- To describe changes from baseline in carotid intima-media thickness (cIMT) after 80 weeks of SC evolocumab, added to standard of care in pediatric subjects 10 to 17 years of age with HeFH or HoFH
- To describe change from baseline in growth and pubertal development parameters at measured timepoints with 80 weeks of SC evolocumab, added to standard of care in pediatric subjects 10 to 17 years of age with HeFH or HoFH

Other Safety Objectives:

- To evaluate the incidence of abnormal neurological examination findings after 80 weeks of SC evolocumab added to standard of care in pediatric subjects 10 to 17 years of age with HeFH or HoFH
- To assess cognitive function, assessed using the change from baseline in the components of the Cogstate battery at each scheduled administration, after 80 weeks of SC evolocumab added to standard of care in pediatric subjects 10 to 17 years of age with HeFH or HoFH

Exploratory Objectives:

- To describe change and percent change at measured timepoints in LDL-C, total cholesterol, non-HDL-C, ApoB, total cholesterol/HDL-C ratio, ApoB/ApoA1 ratio, triglycerides, VLDL-C, HDL-C, ApoA1, lipoprotein(a) [Lp(a)], with 80 weeks of SC evolocumab, added to standard of care in pediatric subjects 10 to 17 years of age with HeFH or HoFH
- To describe change at measured timepoints in proprotein convertase subtilisin/kexin type 9 (PCSK9) and high sensitivity C-reactive protein (hsCRP) with 80 weeks of SC evolocumab, added to standard of care in pediatric subjects 10 to 17 years of age with HeFH or HoFH
- To describe the incidence of abnormal neurological examination findings with 80 weeks of SC evolocumab, added to standard of care in pediatric subjects 10 to 17 years of age with HeFH or HoFH
- To investigate the relationship between novel and established biochemical cardiovascular and lipid biomarkers and effects of evolocumab in pediatric subjects 10 to 17 years of age with HeFH

- In subjects consenting to the optional pharmacogenetics analysis, to investigate potential correlations of study data including the subject response to evolocumab with genetic variation in markers of (PCSK9) signaling, low-density lipoprotein receptor (LDLR) turnover, cholesterol metabolism, inflammation, and plaque stability

Hypothesis: The primary clinical hypothesis is that SC evolocumab will be well tolerated when added to standard of care in pediatric subjects 10 to 17 years of age with HeFH or HoFH

Primary Endpoint: Treatment emergent adverse events at week 80

Secondary Efficacy Endpoints:

- Percent change from baseline at week 80 in:
 - LDL-C
 - non-HDL-C
 - ApoB
 - total cholesterol/HDL-C ratio
 - ApoB/ApoA1 ratio
- Change from baseline in LDL-C at week 80

Secondary Safety Endpoints:

- Change from baseline in steroid hormones (estradiol in females, testosterone in males; follicle-stimulating hormone [FSH], luteinizing hormone [LH], adrenocorticotropic hormone [ACTH], dehydroepiandrosterone sulfate [DHEA-S], cortisol in all subjects) at week 80
- Abnormal muscle and liver enzyme levels (creatinine kinase [CK], aspartate aminotransferase [AST], or alanine aminotransferase [ALT]) at week 80
- Change in cIMT from baseline at week 80
- Change from baseline in growth (height and weight) and pubertal development (Tanner staging) at weeks 24, 48, and 80

Study Design: This is an open-label, single-arm, multicenter study. Subjects are eligible for screening if they have completed Study 20120123 (and did not experience a treatment-related serious adverse event) or if they are 10 to 17 years of age at time of enrollment and have HoFH. The minimum expected enrollment of HeFH rollover subjects is approximately 70% of subjects enrolled in Study 20120123 or approximately 111 subjects. In addition, approximately 10 subjects with HoFH (and without prior participation in an evolocumab study) will be enrolled for an expected total enrollment of approximately 124 subjects. Depending on willingness of subjects completing Study 20120123 to receive open-label evolocumab, final enrollment may be smaller or greater.

Where permitted by local regulations, the study includes collection of biomarker development samples and subjects will be invited to consent/assent to pharmacogenetic analyses.

Sample Size: Approximately 124 subjects are anticipated to enroll in this trial. This corresponds to an estimated 70% rollover for subjects with HeFH from the parent study 20120123 and approximately 10 subjects with HoFH enrolling in this study. Depending on rollover rate from Study 20120123, final enrollment may be smaller or greater.

Summary of Subject Eligibility Criteria: Males and females who have completed Study 20120123 (and did not experience a treatment-related serious adverse event) and males and females of 10 to 17 years of age with diagnosis of HoFH and receiving optimized standard of care lipid-lowering therapy per locally applicable guidelines are eligible for this study. Diagnosis of HoFH must be by genetic confirmation or a clinical diagnosis based on a history of an untreated LDL cholesterol concentration greater than 500 mg/dL (13 mmol/L) together with either xanthoma before 10 years of age in the subject, or evidence of heterozygous familial

hypercholesterolemia in both parents. At screening, HoFH subjects must be on a low-fat diet and receive background lipid-lowering therapy (such as statins, cholesterol absorption inhibitors, bile acid sequestrants, nicotinic acid, or combinations thereof). Lipid-lowering therapy must be stable for ≥ 4 weeks prior to screening. Fasting LDL-C for HoFH subjects must be ≥ 130 mg/dL (3.4 mmol/L) and fasting triglycerides must be ≤ 400 mg/dL (4.5 mmol/L) as determined by the central laboratory at screening.

The following are exclusion criteria for subjects with HoFH (those not rolling over from a prior evolocumab study): estimated glomerular filtration rate (eGFR) < 30 ml/min/1.73m²; CK $> 3x$ ULN; AST or ALT $> 2x$ ULN; (all screening by central laboratory); known active infection or major hematologic, renal, metabolic, gastrointestinal or endocrine dysfunction; subject has taken a cholesterylester transfer protein (CETP) inhibitor in the last 12 months, or mipomersen or lomitapide in the last 5 months prior to LDL-C screening, or has received any therapy to inhibit proprotein convertase subtilisin/kexin type 9 (PCSK9) within 12 weeks prior to screening; subject has a history or evidence of any other clinically significant disorder, condition or disease, or planned or expected procedure that, in the opinion of the Investigator or Amgen physician, would pose a risk to subject safety or interfere with the study evaluation, procedures or completion. The following are major exclusion criteria for all subjects: subjects cannot be receiving treatment in another investigational device or drug study, or less than 30 days since ending treatment on another investigational device or drug study (except Study 20120123); female subjects of childbearing potential cannot be pregnant or breast feeding or planning to become pregnant or planning to breast feed and must be willing to use acceptable method(s) of effective birth control (may include true sexual abstinence) during treatment with evolocumab and for an additional 15 weeks after the end of treatment with evolocumab.

For a full list of eligibility criteria, please refer to [Section 4.1.1](#) through [Section 4.1.2](#).

Amgen Investigational Product Dosage and Administration: Investigational product (evolocumab) will be administered subcutaneously using a spring-based prefilled 1.0 mL autoinjector/pen (AI/Pen) or automated mini-doser (AMD) (upon availability). Each prefilled AI/Pen will contain 140 mg / 1.0 mL deliverable volume of evolocumab. The AMD will contain 420 mg / 3.5 mL deliverable volume of evolocumab. Subjects will have the opportunity to switch between the AI/Pen and AMD at any scheduled time point where evolocumab is supplied to the subject, provided the appropriate supply is available. Dosing will be as follows:

- Evolocumab 420 mg SC QM (3 AI/Pen injections or 1 AMD administration)

Non Amgen Non-investigational Products: Subjects will continue to use stable background lipid lowering therapies as prescribed. These therapies will not be provided by Amgen unless required by law.

Procedures: Subjects who have completed Study 20120123 (and did not experience a treatment-related serious adverse event) and have signed parental/guardian consent/permission and subject consent/assent for Study 20120124, will be enrolled. Subjects with HoFH being considered for participation in this study, and who have signed parental/guardian consent/permission and subject consent/assent, will be assessed for inclusion and exclusion criteria. Medical and medication history will be obtained. Subjects will undergo screening laboratory assessments, including a SC administration of placebo to evaluate tolerability of the SC injection in subjects with HoFH only. Lipid eligibility screening must be conducted after subject has been on a low-fat diet and receiving stable lipid-lowering therapy for ≥ 4 weeks. Subjects should maintain their diet, lipid-lowering therapy, and exercise regimen throughout screening and all phases of study participation. Eligible subjects will start receiving open-label evolocumab, in addition to their background lipid-lowering therapy.

Day 1 is defined as the day of first administration of evolocumab. Subsequent study visits are at weeks 4, 12, 24, 36, 48, 60, 72, and 80 (EOS, end-of-study). Subjects who discontinue IP early for any reason will be asked to continue to return for all other study procedures and measurements until the end of the study.

Adverse Events/Serious Adverse Events/Adverse Device Effects (ADE) and concomitant therapy will be collected at every study visit. Other assessments and procedures are done as per Schedule of Assessments ([Table 2](#)) and include vital signs, dietary instruction, physical exam,

body height and weight, 12-lead electrocardiograms (ECGs), chemistry, hematology, anti-evolocumab antibodies, biomarker sample collection, serum pregnancy testing (females of childbearing potential), urinalysis, specific laboratory assessments, assessment of growth and pubertal development (Tanner staging), carotid intima-media thickness (cIMT), and IP administration. Specific laboratory assessments will include estradiol for girls, testosterone for boys, creatinine phosphokinase, FSH, LH, ACTH, DHEA-S, and cortisol. If the subject consented to pharmacogenetics analyses and DNA has not already been obtained after consenting in Study 20120123, DNA will be extracted from some of the blood samples. IP administration by SC injection, if applicable, will be done after all other procedures have been completed.

For a full list of study procedures, including the timing of each procedure, please refer to [Section 7](#) and the Schedule of Assessments ([Table 2](#)).

Statistical Considerations:

General Considerations

Statistical analyses in this open label study are descriptive in nature. No statistical hypothesis testing or missing value imputation is planned.

Subject disposition, demographics, and baseline characteristics will be summarized. Summary statistics for continuous variables will include the number of subjects, mean, median, standard deviation or standard error, minimum, and maximum. For categorical variables, the frequency and percentage will be given.

For efficacy analyses, the baseline value is defined as:

- Subjects that participated in parent Study 20120123 and with baseline data from the parent study: the baseline is defined as the baseline of the qualifying parent study.
- Subjects not enrolling from a parent study or without baseline data from the parent study: the baseline is defined as the baseline in this study.

The full analysis set (FAS) includes all subjects with HeFH from parent study 20120123 who are enrolled **and dosed**, and all subjects with HoFH who are enrolled and dosed in this study. Analysis of all the endpoints with FAS will be provided. Subjects will be summarized according to whether subject rolled over from a parent study and their treatment allocation from a parent study when applicable.

Interim Analysis and Early Stopping Guidelines

The interim analysis will be conducted when all the enrolled subjects in the study have opportunity to experience 28 weeks of investigation product exposure or have early terminated from the study. At that time, the database related to the interim analyses of the study will be cleaned, processed and a snapshot will be taken. Unless specified otherwise, the FAS will be the default analysis set in this study. Similar to the primary analysis, the interim data will be summarized by cohort (HeFH and HoFH). Statistical analysis in this interim analysis is descriptive in nature for all safety and efficacy endpoints if applicable. No statistical hypotheses testing, or missing value imputation is planned. There is no study stopping rule for either futility or efficacy and the current design or execution of the study will continue without any changes regardless of the result of the interim analysis.

Analysis of Primary Endpoint

Subject incidence of all treatment emergent adverse events will be tabulated by system organ class and preferred term at week 80. Tables of fatal adverse events, serious adverse events, device related adverse events, adverse events leading to withdrawal from investigational product, and significant treatment emergent adverse events will also be provided. Adverse events will be coded using the latest version of Medical Dictionary for Regulatory Activities (MedDRA).

Analyses of Secondary Endpoints

Growth and pubertal development parameters will be summarized at weeks 24, 48, and 80. Other secondary endpoints will be summarized at week 80. Descriptive statistics will be presented.

An independent DMC which is external to Amgen will formally review the accumulating data to ensure there is no avoidable increased risk for harm to subjects.

For a full description of statistical analysis methods, please refer to [Section 10](#).

[figure not shown]
Sponsor: Amgen

Data Element Standards
Version(s)/Date(s):

Version 5 / 20 March 2015

Approved

Study Design and Treatment Schema

Approved

EOS = End of Study; HeFH = Heterozygous Familial Hypercholesterolemia; HoFH = Homozygous Familial Hypercholesterolemia; IP = Investigational Product; QM = every 4 weeks; SC = subcutaneous

Study Glossary

Abbreviation or Term	Definition/Explanation
ADE	Adverse device effect
AE	Adverse event
AI/Pen	Autoinjector/pen
ALP	Alkaline phosphatase
ALT (SGPT)	Alanine aminotransferase (serum glutamic-pyruvic transaminase)
AMD	Automated mini-doser
ApoA1	Apolipoprotein A-1
ApoB	Apolipoprotein B
AST (SGOT)	Aspartate aminotransferase (serum glutamic-oxaloacetic transaminase)
BP	Blood pressure
BUN	Blood urea nitrogen
CAD	Coronary artery disease
CAS	Completer analysis set
CETP	Cholesterylester transfer protein
cIMT	carotid intima-media thickness
CK	Creatine kinase
CHD	Coronary heart disease
CRF	Case report form
CRP	C-reactive protein
CTCAE	NCI Common Terminology Criteria for Adverse Events
DILI	Drug-induced liver injury
DMC	Data monitoring committee (Efficacy and Safety Evaluation Committee)
DNA	Deoxyribonucleic acid
ECG	Electrocardiogram
EDC	Electronic data capture
eGFR	Estimated glomerular filtration rate; eGFR will be calculated by the central laboratory and provided to the investigator.
Electronic Source Data (eSource)	Source data captured initially into a permanent electronic record used for the reconstruction and evaluation of a trial.
End of Follow-up	Defined as when the last subject completes the last protocol-specified assessment in the study
End of Study for Individual Subject	Defined as the last day that protocol-specified procedures are conducted for an individual subject

Approved

Abbreviation or Term	Definition/Explanation
End of Study (primary completion)	The end of the study (primary completion) is defined as the last day on which an enrolled subject in this study completes the end-of-study visit (week 80) or terminates the study early
End of Study (end of trial)	Defined as when the last subject is assessed or receives an intervention for evaluation in the study; if the study includes multiple parts (eg, safety follow-up or survival assessment), the end of study would include these additional parts
End of Treatment	Defined as the last assessment for the protocol-specified treatment phase of the study for an individual subject
EOS	End-of-study (for the individual subject)
eSAE Contingency Report Form	electronic Serious Adverse Event Contingency Report Form; when applicable, this paper based form can be used under restricted conditions (eg, when EDC system is down) and faxed to Amgen
FAS	Full analysis set
FH	Familial hypercholesterolemia
FSH	Follicle-stimulating hormone
GCP	Good Clinical Practice
HCV	Hepatitis C virus
HDL-C	High density lipoprotein cholesterol
HeFH	Heterozygous familial hypercholesterolemia
HoFH	Homozygous familial hypercholesterolemia
HR	Heart Rate
hsCRP	High sensitivity C-reactive protein
IB	Investigator's Brochure
ICF	Informed consent form
ICH	International Council for Harmonisation
IEC	Independent ethics committee
IFU	Instructions for Use
Ig	Immunoglobulin
IM	Intramuscular
IMP	Investigational medicinal product
INR	International normalized ratio
Interactive Voice Response (IVR)	Telecommunication technology that is linked to a central computer in real time as an interface to collect and process information.
Interactive Web Response (IWR)	Web based technology that is linked to a central computer in real time as an interface to collect and process information.
IRB	Institutional Review Board

Approved

Abbreviation or Term	Definition/Explanation
IP	Investigational product (evolocumab, administered with the medical devices used in this study – the prefilled autoinjector/pen [AI/pen] or automated mini-doser [AMD] [upon availability])
IPIM	Investigational Product Instruction Manual
IVRS/IWRS	Interactive Voice Response System / Interactive Web Response System
IV	Intravenous
LDH	Lactate dehydrogenase
LDL-C	Low-density lipoprotein cholesterol
LDLR	LDL receptor
LLN	Lower limit of normal
LOF	Loss of function
Lp(a)	Lipoprotein(a)
MedDRA	Medical dictionary for regulatory activities
NASH	Nonalcoholic steatohepatitis
PCSK9	Proprotein convertase subtilisin/kexin type 9
PD	Pharmacodynamic
PFS	Pre-filled syringe
PI	Principal investigator
PK	Pharmacokinetic
QM	QM is defined as every 4 weeks with a window of ± 3 days for each dose until week 4, then ± 7 days after week 4. Note: day 1 and week 80 visits must be scheduled at approximately the same time of day, and should be performed as close as possible to 8 am as the hormones measured have diurnal variation.
RBC	Red blood cells
SAE	Serious adverse event
SC	Subcutaneous
SoC	Standard of care
Source Data	Information from an original record or certified copy of the original record containing patient information for use in clinical research. The information may include, but is not limited to, clinical findings, observations, or other activities in a clinical trial necessary for the reconstruction and evaluation of the trial. Source data are contained in source documents (original records or certified copies). (ICH Guideline (E6)). Examples of source data include Subject identification, Randomization identification, and Stratification Value.
Study Day 1	Defined as the first day that protocol-specified investigational product is administered to the subject
TBL	Total bilirubin

Approved

Abbreviation or Term	Definition/Explanation
TC	Total cholesterol
TIA	Transient ischemic attack
TNF	Tumor necrosis factor

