10.2 Sample Size Considerations

Approximately **124** subjects are anticipated to enroll in this trial. This corresponds to at least 70% rollover for subjects with HeFH from the parent study 20120123 and at least 10 subjects with HoFH enrolling in this study.

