3.2 Sample Size

Approximately **124** subjects are anticipated to enroll in this trial. This corresponds to an estimated 70% rollover for subjects with HeFH from the parent study 20120123 and approximately 10 subjects with HoFH enrolling in this study. Depending on rollover rate from study 20120123, final enrollment may be smaller or greater.

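### Does it matter that about 111 HeFH plus about 10 HoFH subjects is 121, while the plan expects about 124?

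*Protocol*

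**What the plan says.** The Study Design text of the Protocol Synopsis, repeated in substance in Protocol 3.1 and SAP 3.1, gives the HeFH component: "The minimum expected enrollment of HeFH rollover subjects is approximately 70% of subjects enrolled in Study 20120123 or approximately 111 subjects". It adds about 10 HoFH subjects with no earlier evolocumab study, and these "will be enrolled for an expected total enrollment of approximately 124 subjects".

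The Sample Size paragraph of the synopsis and Protocol 3.3 explain the total this way: "This corresponds to an estimated 70% rollover for subjects with HeFH from the parent study 20120123 and approximately 10 subjects with HoFH". SAP 3.2 agrees: "This corresponds to an estimated 70% rollover for subjects with HeFH from the parent study 20120123", again with about 10 HoFH. Protocol 10.2 uses different qualifiers for the same total: "at least 70% rollover for subjects with HeFH from the parent study 20120123 and at least 10 subjects with HoFH enrolling in this study".

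The number 111 appears only in the Study Design text, where it is a minimum. None of the sentences explaining what 124 corresponds to contains 111. All of these sections except Protocol 10.2 add that final enrolment may fall on either side of the forecast. The size of Study 20120123 is not stated.

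**The concern.** A reader who adds the components gets 121, not 124. These are specific numbers rather than round ones, and the Study Design text presents the total as the result of adding HoFH subjects to the HeFH subjects. The Amendment 4 summary lists 111, 10 and 124 together, so the gap is not left over from mixing versions.

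This is also the only sample-size rationale in the plan. If the three missing subjects were HoFH, that cohort would be 13 rather than 10. HoFH is summarised as its own cohort, so its size affects how much its safety summary can show. The shift between *estimated* and *at least* for 70%, and between *approximately* and *at least* for 10, leaves it unclear whether 124 is a forecast or a floor.

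**Working it through.** **Inputs.** HeFH about 111, called a minimum and set at about 70% of the parent study; HoFH about 10; total about 124 (Protocol Synopsis, 3.1; SAP 3.1). Parent-study N: not given, so a range is assumed below.

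**1. The plan's total.** 111 + 10 = 121. Gap: 124 − 121 = 3, and 3/124 = 2.4%. As a plain sum, 124 is not reproduced.

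**2. What 124 would need.** With 10 HoFH: 124 − 10 = 114 HeFH. With 111 HeFH: 124 − 111 = 13 HoFH. Neither 114 nor 13 appears in the documents.

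**3. The 70% link.** If 111 is exactly 70%, parent N = 111/0.70 = 158.6, and 114/158.6 = 71.9%. If 114 is exactly 70%, parent N = 114/0.70 = 162.9, and 111/162.9 = 68.1%. Over that range:

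| Assumed parent N | 70% of N, plus 10 | 111/N | 114/N |
|---|---|---|---|
| 158 | 120.6 | 70.3% | 72.2% |
| 159 | 121.3 | 69.8% | 71.7% |
| 160 | 122.0 | 69.4% | 71.3% |
| 161 | 122.7 | 68.9% | 70.8% |
| 162 | 123.4 | 68.5% | 70.4% |
| 163 | 124.1 | 68.1% | 69.9% |

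No single N makes both 111 and 114 exactly 70%. Throughout the range, though, both lie within about two percentage points of 70%. The documents therefore do not show that 124 fails to correspond to about 70% rollover.

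**4. What depends on the number.**
- Power or precision: none is calculated. Protocol 10.3.3 and 10.4.1 and SAP 9.1 make all analyses descriptive, with no formal hypothesis tested.
- Denominators: the full analysis set (Protocol 10.1.2, SAP 6) is the subjects enrolled and dosed.
- Timing: the interim and primary analyses (Protocol 10.3.2, 10.3.3) are triggered by follow-up of all enrolled subjects, not by a count.
- Reporting: SAP 9.2 tabulates numbers enrolled, given investigational product, and included in or excluded from the analysis set. SAP 9.1 summarises by cohort.

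**5. Size, if the forecast were used for precision.** The one-sided 95% upper limit with no events is 1 − 0.05^(1/n).
- Total: n = 121 gives 2.45%; n = 124 gives 2.39%.
- Gap in HeFH: n = 111 gives 2.66%; n = 114 gives 2.59%.
- Gap in HoFH: n = 10 gives 25.9%; n = 13 gives 20.6%.

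Only the last pair differs visibly, and it requires 13 HoFH subjects, a number that no section gives. None of these limits is a planned analysis.

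**The case for a change.** The best case for a correction is that calling figures approximate shows the gap is small, not that the sum is right. Reading 111 and 10 as floors reconciles Protocol 10.2 with 124. It does not fit the synopsis Sample Size paragraph, Protocol 3.3 or SAP 3.2, where 70% and 10 are point estimates. If 70% means 111, those sentences lead to 121. A wording correction would cost no patients and would settle the planned size of the HoFH cohort.

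Two parts of this stand: the components sum to 121, and the qualifiers in Protocol 10.2 differ from those elsewhere. So 111 and 124 cannot both be point values from one 70% rollover plus 10 HoFH.

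Three parts do not stand. The figures are not incompatible as written, because none is given as exact and 111 is a minimum. The mismatch with 70% is not shown without the parent-study N. A loss or gain of 30% of the HoFH cohort (3/10) assumes the whole gap lies there, although every statement puts HoFH at about or at least 10 and the text ties the uncertainty in final enrolment to rollover. Placed in HeFH, the gap is 3/111 = 2.7%. The study schema, which the Amendment 4 summary says carries the new enrolment number, was not readable in the text examined, so a cohort split there cannot be ruled out.

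**Conclusion.** This is a clerical slip, and correcting it would gain nothing for the trial. The stated components fall three subjects (2.4%) short of the stated total, and one section words its qualifiers differently. Both are differences between approximate enrolment forecasts in a single-arm descriptive study that takes what rolls over from its parent. Reconciling them would alter no analysis set, analysis timing, summary or conclusion, and the report will show the actual number in each cohort.

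The conclusion rests on the planned number entering no calculation, which holds throughout the Protocol and SAP, and on HoFH being about 10, as every section says. It does not depend on the parent-study size, which was assumed to lie between 158 and 163 only to show that 111 and 114 are both close to 70%.
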